#### 6.12.6. Vital Signs and Other Physical Findings

Postbaseline measurements and change from baseline to postbaseline for vital signs and physical characteristics (systolic blood pressure [SBP], diastolic blood pressure [DBP], pulse rate, weight, BMI) at the scheduled visits will be summarized for patients who have both baseline and at least 1 postbaseline result.

The measurements during the treatment period (0 to 26) will be analyzed by an MMRM model with treatment, baseline value of the response variable, visit, and visit by treatment interaction as fixed factors and patient as the random factor.

Weight during the lead-in period will also be analyzed by an MMRM model with Visit 2 value of the response variable, randomized treatment, visit, and treatment-by-visit interaction as fixed factors and patient as the random factor in all randomized patients.

An ANCOVA model will also be used for the analysis of the last nonmissing observation (including early discontinuation) during the treatment period and during the entire study (up to Visit 801). The ANCOVA models are the same as those used for clinical laboratory measures.

The percentages of patients with treatment-emergent high or low vital signs and weight at any time during the treatment period (0 to 26) or during the entire study including safety follow-up period will be summarized by treatment group for patients who have both baseline and at least 1 postbaseline measurement. A treatment-emergent high result is defined as a change from a value less than or equal to the high limit at all baseline visits to a value greater than the high limit at any time that meets the specified change criteria during the treatment period or during the entire study including safety follow-up period. A treatment-emergent low result is defined as a change from a value greater than or equal to the low limit at all baseline visits to a value less than the low limit at any time that meets the specified change criteria during the treatment period or during the entire study including safety follow-up period. A treatment-emergent low result is defined as a change from a value greater than or equal to the low limit at all baseline visits to a value less than the low limit at any time that meets the specified change criteria during the treatment period or during the entire study including safety follow-up period. Treatment comparison will be based on Fisher's exact test. Table 6.6 will be used to define the low and high limits and change thresholds.

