Safety Laboratory Tests (chemistry, hematology, lipids) – continuous analysis	All Patients in the Safety Population with a baseline and a postbaseline observation	Last of Visits 1-8	Visit 18 (planned) AND Last of Visits 9-18 (planned including early discontinuation visits), regardless of IP use
Safety Laboratory Tests (chemistry, hematology, lipids) – categorical analysis	All Patients in the Safety Population with a normal baseline (with respect to the direction being analyzed) and a postbaseline observation	Visits 1 -8 (including unplanned tests)	Visits 9-18 (including unplanned tests), regardless of IP use

Study	Patient Population	Baseline Observations	Postbaseline Observations
Period/Analysis			
TEAEs	All patients in the Safety Population	Prior to first dose of randomized IP (or Visit 8 date if missing) and after the first dose of open-label insulin lispro (or Visit 2 date if missing)	From first dose of randomized IP to last dose of randomized IP AND From first dose of randomized IP to Visit 801
Hypoglycemia events	All patients in the Safety Population	All Visits 2-8	All Visits 9-18 prior to discontinuation of IP
Weight and vital signs	All Patients in the Safety Population with a baseline and a postbaseline observation	Last of Visits 2-8	Visits 9-18 prior to discontinuation of IP AND Visits 9-801 regardless of IP use
Anti-insulin lispro antibody	Safety Population	Visit 2	Visits 3-801 regardless of IP use

Baseline and Postbaseline Definitions and Patient Po	pulation by Study	v Period and Type of Analysis
Buschne und i ostbuschne Demittons und i utent i	pullution by Stud	j i ci ioù una i jpe oi i inaijsis

Abbreviations: 1,5-AG = 1,5-Anhydroglucitol; ANCOVA = analysis of covariance; EQ-5D-5L = European Quality

of Life- 5 Dimensions 5 Level; EQ-VAS = EuroQol visual analogue scale; HbA1c = hemoglobin A1c; IP = investigational product; ITSQ = Insulin Treatment Satisfaction Questionnaire; ITT = intention-to-treat; LOCF = last-observation-carried forward; MMTT = mixed meal tolerance test; MMRM = mixed-effect model repeated measures; SMBG = self-monitored blood glucose; TEAE = treatment-emergent adverse event; WPAI-GH = Work Productivity and Activity Impairment General Health.

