#### 6.12.5. Clinical Laboratory Evaluation

The data from safety laboratory measures will be summarized at Week 26 where the lab test is planned to be collected. Postbaseline and change from baseline to postbaseline for laboratory tests will be summarized for patients who have both baseline and at least 1 postbaseline result and compared between treatment groups by using ANCOVA model with the term of treatment and baseline value of the response variable. Analyses will be provided in SI units.

The last nonmissing observation at or prior to Week 26 (planned tests including early discontinuation) will also be analyzed by an ANCOVA model with the term of treatment, baseline value of the response variable.

The percentages of patients with treatment-emergent abnormal, high, or low laboratory results at any time during the treatment period (0 to 26) will be summarized for patients who have both baseline and at least 1 postbaseline result and compared between treatment groups using Fisher's exact tests. A treatment-emergent abnormal result is defined as a change from normal at all

baseline visits to abnormal at any time during the treatment period. A treatment-emergent high result is defined as a change from a value less than or equal to the high limit at all baseline visits to a value greater than the high limit at any time during the treatment period. A treatment-emergent low result is defined as a change from a value greater than or equal to the low limit at all baseline visits to a value less than the low limit at any time during the treatment period. A treatment-emergent visits to a value less than the low limit at any time during the treatment period. Planned and unplanned measurements will be included. **CC** be used to define the low and high limits. Only patients who have normal baseline values for the analysis being performed will be included in the analysis for treatment-emergence.

Liver enzymes measures will not be included in the above analyses as different analyses will be used as described in Section 6.12.4.4.2 and Section 6.12.4.4.3.

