# Table 6.6.Categorical Criteria for Abnormal Treatment-Emergent Blood
Pressure and Pulse Measurement, and Categorical Criteria for
Weight Changes for Adults

Parameter	Low	High
Systolic BP (mm Hg)	$\leq$ 90 and decrease from baseline $\geq$ 20	≥140 and increase from baseline
(Supine or sitting – forearm		$\geq 20$
at heart level)		
Diastolic BP (mm Hg)	$\leq$ 60 and decrease from baseline $\geq$ 10	$\geq$ 90 and increase from baseline $\geq$ 10
(Supine or sitting – forearm		
at heart level)		
Pulse (bpm)	<60 and decrease from baseline ≥15	>100 and increase from baseline
(Supine or sitting)		≥15
Weight (kg)	(Loss) decrease ≥7%	(Gain) increase ≥7%
(Consistent clothing and		
timing in relationship to		
meals and voiding)		

Abbreviations: BP = blood pressure.

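### Treatment-emergent blood pressure and pulse percentages keep in the denominator patients who cannot become events, unlike the SAP's own laboratory rule

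*SAP*

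**What the plan says.** SAP 6.12.6 gives this definition of a treatment-emergent high vital sign: "change from a value less than or equal to the high limit at all baseline visits to a value greater than the high limit". The mirror definition applies to a low one: "change from a value greater than or equal to the low limit at all baseline visits to a value less than the low limit". In both cases the value must also meet a change criterion, and "Table 6.6 will be used to define the low and high limits and change thresholds". The percentages, for the treatment period and for the whole study including follow-up, "will be summarized by treatment group for patients who have both baseline and at least 1 postbaseline measurement". Table 6.2 has a single row for weight and vital signs, whose population is "All Patients in the Safety Population with a baseline and a postbaseline observation".

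For laboratory tests, SAP 6.12.5 starts from the same population and an equivalent event definition, then adds a restriction: "Only patients who have normal baseline values for the analysis being performed will be included in the analysis for treatment-emergence". Table 6.2 splits laboratory tests into a continuous and a categorical row. The categorical row repeats the restriction: "All Patients in the Safety Population with a normal baseline (with respect to the direction being analyzed) and a postbaseline observation". Neither the rest of 6.12.6 nor Table 6.6 supplies a matching restriction for vital signs.

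**The concern.** Numerator and denominator are drawn from different groups. A patient with a high systolic value at any baseline visit is barred from the numerator for high systolic pressure, whatever happens on treatment, but still adds one to the denominator. The output therefore mixes patients who did not have the event with patients who could not have it.

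Two things follow. The percentage is lower than the incidence among patients at risk. And the label treatment-emergent means one thing in the laboratory tables and another in the vital-sign tables of the same report, with no reason given.

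Vital signs are a listed safety endpoint. LY900014 contains treprostinil, and Protocol 3.3 lists hypotension and vasodilatation among the effects of its systemic absorption, so these tables will be read. The same section says treprostinil cannot be measured in serum at the LY900014 doses expected in clinical use, so this is about reporting the tables correctly and does not point to an expected signal.

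**Working it through.** The documents state no treatment-emergent vital-sign incidence and no share of patients with abnormal baselines, so there is no plan figure to reproduce.

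**Inputs**
- Numerator, denominator and test (Fisher's exact): SAP 6.12.6.
- Limits: SAP Table 6.6.
- Baseline readings: the Schedule of Activities has vital signs at Visits 2, 5, 7 and 8 within the Visit 2 to 8 window of Table 6.2.
- Size, for illustration only: about 350 randomized 1:1, so 350 / 2 = 175 per arm (SAP 5.2).
- q: not in the documents; assumed 5% to 30%.

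**Identity.** For one parameter and direction, let N be the patients with a baseline and a postbaseline value, A those among them abnormal in that direction at baseline, and E the events. All E come from the N − A. Then

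E/N = [E/(N − A)] × (1 − A/N), that is, reported % = at-risk % × (1 − q), with q = A/N.

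**Effect on a percentage** (at-risk incidence 10%):

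| q (assumed) | Reported | At-risk / reported = 1/(1 − q) |
|---|---|---|
| 0% | 10.0% | 1.00 |
| 5% | 9.5% | 1.05 |
| 10% | 9.0% | 1.11 |
| 15% | 8.5% | 1.18 |
| 20% | 8.0% | 1.25 |
| 30% | 7.0% | 1.43 |

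**What drives q.** One abnormal reading at any baseline visit is enough, so q grows with the number of visits. In a simulation with an assumed systolic mean of 125, between-patient SD 12 and within-patient SD 9, the share above 140 is about 15% on one reading and 32% on four. For low systolic pressure and high pulse, assumed distributions gave only about 5% to 6% on four readings. All of these move with the assumed means and SDs.

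**Effect on the between-arm comparison** (hypothetical counts, q equal in both arms):

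| Events | All patients, 175 per arm | At risk, q = 20%, 140 per arm | At risk, q = 30%, 123 per arm |
|---|---|---|---|
| 8 vs 16 | 4.6% vs 9.1%, p = 0.137 | 5.7% vs 11.4%, p = 0.134 | 6.5% vs 13.0%, p = 0.131 |
| 5 vs 14 | 2.9% vs 8.0%, p = 0.057 | 3.6% vs 10.0%, p = 0.055 | 4.1% vs 11.4%, p = 0.054 |

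The ratio between arms does not change.

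**Chance imbalance in q.** The standard error of the between-arm difference in q is √(2q(1 − q)/175). At q = 20% it is √(2 × 0.20 × 0.80/175) = 4.3 points, which shifts an equal 10% incidence by 0.10 × 4.3 = 0.43 points. At q = 5.5% it is 2.4 points, a shift of 0.24 points. An imbalance of 15% versus 25% would show equal 10% incidences as 8.5% versus 7.5%, but it lies about 2.3 standard errors out (10/4.3) and is not typical.

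**The case against.** The all-patient percentage is a legitimate quantity: the share of evaluable patients with a newly emergent abnormality. The SAP does much the same for adverse events, where a patient already at maximum baseline severity for a term stays in the Safety Population denominator. A reader might infer that the vital-sign denominator is simply an error. The documents do not go that far: they show an unexplained difference between two neighbouring analyses, and a percentage that is low relative to an at-risk denominator. That narrower statement stands.

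A reader might also take the Table 6.2 vital-signs row as independent confirmation. It is weak evidence. That one row also has to serve the MMRM and ANCOVA analyses, where a normal-baseline restriction would be out of place, and its wording matches the laboratory continuous row. The point rests on the text of 6.12.6 set against 6.12.5.

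Finally, a reader might infer that a vasodilator effect would be hidden or the treatment comparison distorted. The material does not support that. For low systolic pressure and high pulse the assumed q is only about 5% to 6%, so an at-risk 10% is reported as 9.4% to 9.5%. The Fisher result barely changes, and mean shifts in blood pressure and pulse are analysed separately with baseline adjustment.

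**Conclusion.** The point holds for systolic pressure, diastolic pressure and pulse, by direction: a patient with a high baseline can still be a low event. It does not apply to weight, for which Table 6.6 gives only a 7% change and no absolute limit.

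The factor (1 − q) is exact arithmetic; its size is not known from the documents. It is zero if nobody is abnormal at baseline and, on the assumed 5% to 30%, a relative understatement of the same 5% to 30%. The error can only go in the reassuring direction. The consequence is limited to descriptive safety percentages and their consistency with the laboratory tables. Between-arm inference is essentially unaffected when q is balanced, and sample size, alpha and all primary and multiplicity-adjusted results are untouched. It is a minor but cheap correction.

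**What to change.** - **SAP 6.12.6.** State that, for the categorical treatment-emergent analysis of systolic pressure, diastolic pressure and pulse, the denominator for each parameter and direction is patients who meet the numerator's baseline condition (not abnormal in that direction at any baseline visit, using the Table 6.6 limits) and have at least 1 postbaseline measurement. Leave weight on all patients with a baseline and a postbaseline value.
- **Table 6.2.** Add a separate categorical vital-signs row with this population and leave the existing row for the MMRM and ANCOVA analyses.
- **One baseline definition.** Table 6.2 takes the last value from Visits 2 to 8, while 6.12.6 looks at all baseline visits. Reconcile these in the new row. If the denominator used only the last value and the numerator all visits, a patient abnormal at Visit 5 and normal at Visit 8 would still be counted as event-free with no possibility of an event.
- **One boundary rule.** Table 6.6 uses inclusive blood pressure limits, while 6.12.6 requires a value beyond the limit. Settle this too, so that a reading exactly on the limit is treated alike in numerator and denominator.

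The cost is a sentence, a table row and a denominator flag of the kind the laboratory analysis already needs. The downside is small: denominators will differ by parameter and direction, and percentages will look slightly less favourable. If the sponsor prefers the all-patient denominator, the SAP should say so and give the reason for departing from 6.12.5.

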# Table 6.6.Categorical Criteria for Abnormal Treatment-Emergent Blood
Pressure and Pulse Measurement, and Categorical Criteria for
Weight Changes for Adults

Parameter	Low	High
Systolic BP (mm Hg)	$\leq$ 90 and decrease from baseline $\geq$ 20	≥140 and increase from baseline
(Supine or sitting – forearm		$\geq 20$
at heart level)		
Diastolic BP (mm Hg)	$\leq$ 60 and decrease from baseline $\geq$ 10	$\geq$ 90 and increase from baseline $\geq$ 10
(Supine or sitting – forearm		
at heart level)		
Pulse (bpm)	<60 and decrease from baseline ≥15	>100 and increase from baseline
(Supine or sitting)		≥15
Weight (kg)	(Loss) decrease ≥7%	(Gain) increase ≥7%
(Consistent clothing and		
timing in relationship to		
meals and voiding)		

Abbreviations: BP = blood pressure.

#### 6.12.7. Immunogenicity

Blood samples for immunogenicity testing will be collected to determine antibody production against insulin lispro for all enrolled patients since Visit 2 prior to the first dose of study-provided prandial insulin treatment. Therefore, the blood sample result at Visit 2 will be considered as the anti-insulin lispro level at baseline for this study.

#### 6.12.7.1. Treatment Emergent Anti-Insulin Lispro Antibody

The treatment-emergent anti-insulin lispro antibody (denoted as treatment-emergent antidrug antibody [TEADA] throughout this SAP) is based on the change from baseline (Visit 2) to postbaseline (post-Visit 2) in the anti-insulin lispro antibody level (percent binding). Treatment-emergent antidrug antibody can be sub-classified as either treatment-induced (not detected anti-insulin lispro antibody at baseline) or treatment-boosted (detected anti-insulin antibody at baseline):

The TEADA status during a specific analysis period will be determined using all data in the corresponding analysis period regardless of IP use. The summary for TEADA status and the anti-insulin lispro antibody level will use the same analysis data.

The number and percentage of patients with positive TEADA response during the analysis period of Visit 2 to Visit 801 will be summarized by treatment group. For patients with positive TEADA response anytime during the analysis period, the number and percentage of patients with positive

insulin cross-reactivity anytime during the analysis period, and the number and percentage of patients not meeting the TEADA criteria at Visit 801 will also be summarized by treatment group. Treatment groups will be compared by Fisher's exact test.

Both actual and change from baseline (Visit 2) for the anti-insulin lispro antibody level in percent binding will be summarized by scheduled visit prespecified in the protocol for patients with positive TEADA response from Visit 2 to Visit 801. The repeated measurement from Visit 2 to Visit 801 will be analyzed by an MMRM model with treatment, baseline value of the response variable, visit, and visit by treatment interaction as fixed factors and patient as the random factor. The ANCOVA model using treatment and baseline value as covariates will be used for the analysis of last non-missing observation prior to or at Visit 801 and the analysis of maximum percent binding during the analysis period of Visit 2 to Visit 801. Plot of anti-insulin lispro antibody percent binding will be generated based on the MMRM and the ANCOVA models.

A listing of anti-insulin lispro antibody at each visit will be provided. The listing will include antiinsulin lispro antibody status (detected/not detected), anti-insulin lispro antibody percent binding, TEADA status (positive/negative), insulin cross-reactivity status, insulin cross-reactivity percent binding for the safety population.

Subgroup analysis for the following selected efficacy and safety variables will be performed by the TEADA status during the treatment period of Visit2 to Visit 801:

- Use data prior to discontinuation of IP:
  - HbA1c and change from baseline in HbA1c
  - 1-hour and 2-hour PPG excursions
  - o basal, prandial, and total insulin dose
  - event rate (per patient per year) of overall hypoglycemic events
- Use all data regardless of IP use:
  - o treatment-emergent injection site reaction and hypersensitivity reaction

The analyses for HbA1c and change from baseline in HbA1c will be performed using an MMRM model for the primary analysis and the HbA1c data prior to discontinuation of IP. The model will include additional fixed terms of subgroup, subgroup by treatment interaction, subgroup by visit interaction, and 3-way interaction of treatment, subgroup, and visit.

The PPG excursions will be analyzed by the ANCOVA model same as the model specified in Section 6.11.2. with data collected before permanent discontinuation of IP. The model will include additional terms of subgroup, subgroup by treatment interaction, subgroup by visit interaction, and 3-way interaction of treatment, subgroup, and visit.

The subgroup analysis for insulin dose will use the MMRM model specified in Section 6.11.5 using data collected before permanent discontinuation of IP. The model will include additional fixed terms of subgroup, subgroup by treatment interaction, subgroup by visit interaction, and 3-way interaction of treatment, subgroup and visit.

The treatment emergent injection site reaction and hypersensitivity reaction will be analyzed by a logistic regression model including terms of treatment, subgroup, and treatment by subgroup interaction. All data regardless of IP use will be used for this analysis.

The negative binomial regression model specified in Table 6.5 with additional terms of subgroup, treatment by subgroup interaction will be used for the subgroup analysis of overall hypoglycemia event rate while on IP.

The interaction effects (3-way for MMRM and 2-way for ANCOVA/logistic regression model/negative binomial regression model) will be evaluated using a significance level of 0.10, unadjusted. If the interaction effect is significant (p<0.10), separate analyses without the terms related to the subgroup will be performed for each subpopulation.

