The definitions of baseline and postbaseline for the efficacy and safety analyses depend on which analysis period is being used. The following analysis periods will be used:

- Lead-in Period Visits 2-8
- 26-Week Treatment Period from randomization to Week 26 prior to discontinuation of IP
- 26-Week Treatment Period and Safety Follow-Up Visit from randomization to Visit 801 (including all data regardless of IP use)

The data on IP is defined based on the following rules:

- for data only measured at an office visit
  - MMTT postbaseline data will be considered as data on IP if the MMTT performance date is on or prior to the last IP dose date
  - Other postbaseline data (for example, vital signs, laboratory tests, and questionnaires) will be considered as data on IP if the measurement date is on or prior to the cutoff date defined as 14 days after the last IP dose date
- for data collected as running records with an exact date stamp such as adverse events (AEs) and diary entries where the dates of the measures were not tied with the date of an office visit, postbaseline data with dates ≤ (last study drug dose date +1) will be considered as data on IP.

Table 6.2 describes the rules for determining the patient population, baseline and postbaseline observations for the different analysis periods.

For continuous measures, summary statistics will include sample size, mean, SD, median, minimum, and maximum for both the actual and the change from baseline measurements. Least-squares (LS) means and standard errors derived from the analysis models will also be displayed. Treatment comparisons will be displayed showing the treatment difference LS means and the 95% CIs for the treatment differences, along with the p-values for the treatment comparisons.

For categorical measures, summary statistics will include sample size, frequency, and percentages. Fisher's exact test will be used for treatment comparisons.

For laboratory values, Systeme International (SI) units will be presented. Therefore, both % and mmol/mol will be presented for HbA1c and mmol/L will be presented for glucose measurements.

All baseline measures will be analyzed using an analysis of variance (ANOVA) model that has treatment as the model terms.

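### The between-arm comparison of treatment-emergent antibodies counts responses already present in the pre-randomization Visit 8 sample

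*SAP*

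**What the plan says.** The protocol lists a between-arm comparison of treatment-emergent anti-insulin lispro antibody incidence as a tertiary objective (Table ITSD.1). Section 10.3.4 leaves the immunogenicity methods to the SAP.

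- **Reference level.** SAP 6.12.7: "the blood sample result at Visit 2 will be considered as the anti-insulin lispro level at baseline for this study".
- **Postbaseline window.** The antibody row of SAP Table 6.2: "Visits 3-801 regardless of IP use".
- **Count and test.** SAP 6.12.7.1 gives the number and percentage with "positive TEADA response during the analysis period of Visit 2 to Visit 801 will be summarized by treatment group". Status needs to be met only once: "For patients with positive TEADA response anytime during the analysis period". Then: "Treatment groups will be compared by Fisher's exact test".
- **Status by period.** The same section provides that "The TEADA status during a specific analysis period will be determined using all data in the corresponding analysis period regardless of IP use". The only period it goes on to name for TEADA is Visit 2 to Visit 801.
- **Periods defined elsewhere.** SAP 6.1 lists "Lead-in Period Visits 2-8" and, separately, "26-Week Treatment Period and Safety Follow-Up Visit from randomization to Visit 801 (including all data regardless of IP use".

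The protocol's Schedule of Activities places antibody samples at Visits 2, 8, 10, 11, 15, 18, 801 and early discontinuation. Its footnote c puts randomization after all Visit 8 procedures. Protocol 7.2.1.4 has all patients on insulin lispro throughout the lead-in.

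**The concern.** The comparison is meant to show whether LY900014 induces or boosts antibodies more often than insulin lispro. A response first seen at Visit 8 arises under lead-in lispro that everyone receives, before the arms exist. Once positive at Visit 8, a patient stays an event for the whole period, so that patient carries no information about the arm difference.

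Neither arm is favored, because these events are balanced in expectation. What can be lost is sensitivity: both incidences rise by a common amount and the contrast shrinks. In a safety comparison that is the unhelpful direction, since an excess becomes harder to see.

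The window also sits oddly with the rest of the plan. Protocol 10.3.4 names lispro antibodies among the safety measures and describes those analyses as using data from randomization through Week 26. For adverse events, SAP Table 6.2 treats the lead-in as baseline for the randomized comparison, and Table 6.4 reports the lead-in under open-label lispro. SAP 6.12.7 gives a reason for the Visit 2 reference level but none for counting pre-randomization responses by arm.

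**Working it through.** **Placing the samples.** The antibody row of the schedule has exactly one scheduled sample after the Visit 2 baseline and before randomization, at Visit 8. It lies inside the Visits 3-801 window, so it enters the count.

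**The plan's own figure.** There is none to reproduce. The documents give no TEADA rate and no power for this comparison; the only stated power is for HbA1c. Every rate below is an assumption.

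**Inputs.** About 350 patients randomized 1:1 (SAP 5.2), so 175 per arm; two-sided alpha 0.05 (SAP 6.1); Fisher's exact test. Let L be the share already positive at Visit 8, and p the rate of new TEADA after randomization among the rest.

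**Illustration 1: all-or-none conversion.**

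- Counted rate as planned: L + (1 − L)p, with 175 per arm.
- Counted difference: (1 − L)(p₂ − p₁), so the true difference shrinks by the factor 1 − L.
- With Visit 8 positives set aside: rate p, with 175(1 − L) per arm, rounded down.

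Exact Fisher power for p = 10% (insulin lispro) and 20% (LY900014):

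| L | Counted rates as planned | Power as planned | n per arm, Visit 8 positives set aside | Power, set aside |
|---|---|---|---|---|
| 0 | 10.0% and 20.0% | 71% | 175 | 71% |
| 1% | 10.9% and 20.8% | 68% | 173 | 70% |
| 3% | 12.7% and 22.4% | 62% | 169 | 69% |
| 5% | 14.5% and 24.0% | 57% | 166 | 68% |
| 10% | 19.0% and 28.0% | 46% | 157 | 65% |

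With p = 20% and 30%, the two powers are 49% and 52% at L = 3%, and 39% and 49% at L = 10%.

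The share of counted events that precede randomization is L / [L + (1 − L)p]. At L = 3% this is 0.03/0.127 = 24% in the lispro arm and 0.03/0.224 = 13% in the LY900014 arm.

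For scale, a constant hazard giving 10% in 26 weeks implies 1 − 0.9^(8/26) = 3.2% in the 8-week lead-in. L = 10% would need a higher early rate.

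**Illustration 2: TEADA as a threshold on cumulative change from Visit 2.** Lead-in rise N(0.5, 1); later rise N(0.5, 1) for lispro and N(1.0, 1) for LY900014; threshold 2.5. Then L = 2.3%.

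| Rule | Lispro | LY900014 | Power |
|---|---|---|---|
| As planned | 14.9% | 24.2% | 54% |
| Visit 8 positives set aside (171 per arm) | 12.9% | 22.4% | 59% |
| Reference level moved to Visit 8 | 2.3% | 6.7% | 41% |

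The last row shows why moving the reference level to Visit 8 is not the remedy: it misses patients whose rise builds up across both periods.

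**Type I error.** With a true rate of 10% in both arms, the planned test rejects in 3.2%, 3.5% and 3.6% of trials at L = 0, 3% and 10%. With Visit 8 positives set aside (169 per arm) it rejects in 3.2%. Neither rule exceeds 5%.

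**The case against.** The strongest defense is that the window is deliberate. The lead-in, the comparator and the test product all contain insulin lispro, and the assay measures anti-lispro antibody. Counting everything after Visit 2 describes the immunogenicity of all study-provided lispro, and SAP 6.12.2 likewise defines treatment emergence from the first study-provided prandial insulin, open-label lispro included. This stands as a reason for the Visit 2 reference level and for reporting the full-period incidence. It does not explain why that incidence should carry the between-arm test.

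Second, the effect may be negligible. All patients have used insulin for at least a year and prior lispro users are eligible (Protocol 6.1), so few may convert in 8 weeks. Higher assumed rates also shrink the loss: with 30% and 45% at L = 3%, power is 76.9% as planned and 78.4% with Visit 8 positives set aside. This stands, and it is why the point is minor.

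Third, the filter does not isolate post-randomization change. In the threshold illustration, 86% of the lispro-arm events it keeps and 76% of the LY900014-arm events would not reach the threshold on later change alone. That is true, but whether those patients cross still depends on what happens after randomization, so they carry information about the arms. A Visit 8 positive cannot.

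Fourth, the by-visit level summaries, the repeated-measures model in TEADA-positive patients and the by-visit listing would let a reader see Visit 8 values. They do, but they leave the Fisher count unchanged.

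**Conclusion.** The concern holds and is minor. The only TEADA incidence comparison in the SAP includes a pre-randomization sample, so any Visit 8 positive is credited to an arm assigned afterwards. The consequence is dilution toward no difference, without directional bias and without type I error above 5%.

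The size cannot be fixed from the documents. Under the assumed 10% and 20%, the power lost is about 2 to 3 points at L = 1%, 7 at L = 3% and 19 at L = 10%. It is smaller at higher underlying rates and nil at L = 0. No primary or multiplicity-adjusted result depends on this comparison. That the window includes Visit 8 follows from the documents alone; the power figures rest entirely on assumed rates and conversion models.

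**What to change.** In SAP 6.12.7.1:

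1. Keep Visit 2 as the reference level.
2. Base the between-arm Fisher test on patients not TEADA-positive at Visit 8. Count TEADA first met on samples in the period SAP 6.1 already defines from randomization to Visit 801 (Visits 10, 11, 15, 18, 801 and early discontinuation).
3. State how a missing Visit 8 sample is handled, for example by keeping the patient and reporting the number per arm.
4. Report lead-in conversions separately.
5. Keep the Visit 2 to Visit 801 incidence as a supplementary description of total study lispro exposure.
6. Align the antibody row of Table 6.2 with this.

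The cost is SAP wording and one filter. The Visit 8 sample is already scheduled and TEADA status at each visit is already to be listed. Because the filter uses a sample taken before randomization, the comparison remains a randomized one. The price is a slightly smaller denominator (175 × 0.03, about 5 per arm at L = 3%), and any further boosting in lead-in converters would be described but not tested.
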